5. SAMPLE SIZE CONSIDERATIONS

This study is planned to enroll up to 180 subjects. This study is not designed to test a formal null hypothesis. Rather, it is intended to obtain sufficient data to obtain meaningful estimates of the immune response and to uncover any safety issues that occur at a sufficiently high rate that they might be observed in a study of this size. As such, the type I error rate, $\alpha = 0.05$, is not adjusted for multiple comparisons. While this study is not designed to test any specific null hypothesis, the following tables illustrate the precision and power that is available for select estimates and comparisons of interest.

[Table 6](#) indicates the probability of observing one or more safety events, such as solicited injection site or systemic reactogenicity events or an unsolicited non-serious AE of a particular type for a single study group ($N = 30$), or in the trial as a whole ($N=180$).

Binomial confidence intervals (CI) are widest (have the least precision) when the response rate is 50%.

[Table 7](#) is presented to indicate the worst-case scenario for precision of observed exact (Clopper-Pearson) binomial confidence intervals.

[Table 8](#) illustrates the minimum detectable differences in the proportion of subjects responding (e.g. attaining seroconversion or a titer $\geq 1:40$) between any two study groups ($N=30$) using a two-sided Likelihood Ratio Test and $\alpha = 0.05$. It is assumed that up to 10% of subjects ($N=3$) will be excluded from the per protocol analysis. Seroconversion rates of 10% to 50% are considered.

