8.3.2. HAI and Neut Regression Modeling

Regression modeling will be utilized to test for the effect of treatment variables i.e. prime boost combination (*PrimeBoost*), Boost dose (*BoostDose*), and interval between vaccinations (*Interval*), on immune response. Logistic regression will be fit for the seroconversion outcome. If the available titer data meet the required assumptions of normality after log transformation, multiple linear regression will be fit to log-transformed titers. Separate models will be fit for each assay (HAI, Neut), each strain (2013 A/H7N9, 2017 A/H7N9) and each time point (Day 22 post vaccination 1, Day 22 post vaccination 2, Day 181 post vaccination 2). All models will be fit with a similar structure for *PrimeBoost*, *BoostDose*, *Interval*, and covariates, for the PP population. The treatment variables will be defined as *PrimeBoost* (homologous, heterologous), *BoostDose* (3.75 mcg+AS03, 15 mcg), and *Interval* (21 days, 120 days). All models will be fit with and without adjustment for the following covariates (*Z*): age in years, sex (female, male), BMI (<30, ≥ 30), and prior receipt of seasonal influenza vaccine in the current season (did not receive 2018-2019 seasonal influenza vaccine, received 2018-2019 seasonal influenza vaccine) (did not receive 2016-2017 or 2017-2018 seasonal influenza vaccines, received 2016-2017 and/or 2017-2018 seasonal influenza vaccine). The models as shown below assume a linear relationship between age in years and both probability of seroconversion and GMT. The validity of this assumption will be assessed prior to analysis and, if the relationship between age and response is found to be non-linear, adjustments will be made to model parameters to satisfy regression assumptions. Modeling assumptions will be checked using standard diagnostic methods (e.g., using the INFLUENCE option in PROC LOGISTIC or PROC GLM). Parameter estimates and odds ratio estimates for the logistic models will be presented for the 2013 and 2017 A/H7N9 strains without covariate adjustment in Table 64, Table 65, Table 66, Table 67, and with covariate adjustment in Table 68, Table 69, Table 70, Table 71. Parameter estimates for the multiple linear regression models will be presented for the 2013 and 2017 A/H7N9s strain without covariate adjustment in Table 72, Table 73, Table 74, Table 75, and with covariate adjustment in Table 76, Table 77, Table 78, Table 79.

Model 1A: Logistic Regression (without covariate adjustment):

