9.3.1. Solicited Events and Symptoms

Systemic solicited adverse events were collected pre-vaccination, and systemic and local solicited adverse events were collected at-least 20 minutes post-vaccination and then daily for 7 days after each vaccination and graded on a scale of 0 (absent), 1 (mild), 2 (moderate) and 3 (severe). Systemic events include fever, feverishness, fatigue, malaise, myalgia, arthralgia, headache, and nausea. The grading scale for systemic events, including quantitative grading for fever, is included in [Table 11](#). Local events include pruritus, ecchymosis, erythema, induration/swelling, pain, and tenderness. Ecchymosis, erythema, and induration are measured by both functional and measurement grading scales as defined in [Table 10](#).

When calculating the incidence of solicited events, each subject will be counted once at the highest severity following the applicable vaccination, and any repetitions will be ignored. For summaries presented separately for each vaccination, the denominator for percentages will be the number of subjects who received the respective vaccination with non-missing data for the event summarized. For summaries over all vaccinations the denominator will be the number of subjects who received at least one vaccination with non-missing data for the event summarized.

The number and percentage of subjects reporting at least one solicited adverse event of each severity will be summarized for each solicited symptom, any systemic symptom, any local symptom, and any symptoms. For each event the denominator is the number of subjects who received the applicable vaccination with non-missing data for the specific event. The 95% CI calculated using Clopper-Pearson methodology from a binomial distribution (SAS Proc Freq with a binomial option) will be presented ([Table 84](#), [Table 85](#), [Table 86](#)). Logistic regression models will be fit to estimate the effect of prime-boost combination (*PrimeBoost*), Boost dose (*BoostDose*), and interval between vaccinations (*Interval*) on the probability of reporting any local event or reporting any systemic event after either vaccination ([Table 87](#), [Table 88](#)). If statistically significant effects are observed in the model for local events or systemic events, then additional models will be fit for each individual event of that type.

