$$\text{logit}[P(\text{Event})] = \beta_0 + \beta_1 \times \text{PrimeBoost} + \beta_2 \times \text{BoostDose} + \beta_3 \times \text{Interval} + \beta_4 \times (\text{PrimeBoost} * \text{BoostDose}) + \beta_5 \times (\text{PrimeBoost} * \text{Interval}) + \varepsilon,$$

For each systemic and local event, any systemic event, any local event, and any solicited event, the maximum severity over 7 days after each vaccination will be summarized for the Safety population. The number and percentage of subjects reporting each event will be summarized by the maximum severity and study group, separately for each vaccination and over both vaccinations. For each event the denominator is the number of subjects who received the applicable vaccination with non-missing data for the specific event. The 95% CI calculated using Clopper-Pearson methodology from a binomial distribution (SAS Proc Freq with a binomial option) will be presented ([Table 89](#), [Table 90](#), [Table 91](#)).

The number of subjects reporting a solicited adverse event will be summarized for each day post vaccination for each vaccination and for both vaccinations combined both in a summary table ([Table 92](#), [Table 93](#), [Table 94](#)) and graphically in a bar chart ([Figure 26](#) and [Figure 27](#)). A comparison of the event rate for each study group between study vaccinations will be presented, including p-values from McNemar's test performed ([Table 95](#), [Table 96](#)).

Systemic and Local solicited events reported by subject will be presented in [Listing 11](#) and [Listing 12](#), sorted by subject ID, vaccination number, parameter, and study day.

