| | n | % (95% CI) | n | % (95% CI) | n | % (95% CI) | n | % (95% CI) | n | % (95% CI) | n | % (95% CI) | n | % (95% CI) |
| N = Number of subjects in the Safety Population who received any study vaccination; n = Number of subjects reporting event 95% CI estimated using the Clopper-Pearson exact method | | | | | | | | | | | | | | |

Tables with similar format:

Table 85: Number and Percentage of Subjects Experiencing Solicited Events with 95% Confidence Intervals by Symptom and Study Group (Safety Population) – Post Study Vaccination 1

[Footnote update] N = Number of subjects in the Safety Population who received the first study vaccination.

Table 86: Number and Percentage of Subjects Experiencing Solicited Events with 95% Confidence Intervals by Symptom and Study Group (Safety Population) – Post Study Vaccination 2

[Footnote update] N = Number of subjects in the Safety Population who received the second study vaccination.

Table 87: Logistic Regression Model to Evaluate the Relationship of Study Vaccination with Reporting Any Local Event Post Second Study Vaccination, Safety Population

[Implementation Note: If statistically significant effects (defined as p-value <0.05) are observed in the model for local events then this table should be repeated for additional models which will be fit for each individual local event. Any solicited local event grade 1 or higher reported within 7 days of study vaccination will count as a reported event.]

| Model Parameter | Parameter Category | Parameter Estimate | SE | p-value | Odds Ratio | 95%CI |
|-----------------|------------------------|--------------------|-------|---------|------------|-----------|
| Intercept | N/A | xxx.x | xxx.x | x.xxx | - | - |
| Prime-boost | Homologous (reference) | - | - | - | - | - |
| | Heterologous | xxx.x | xxx.x | x.xxx | xx.x | xx.x-xx.x |
| Boost Dose | 15 mcg (reference) | - | - | - | - | - |
| | 3.75 mcg + AS03 | xxx.x | xxx.x | x.xxx | xx.x | xx.x-xx.x |
| Interval | 21 days (reference) | - | - | - | - | - |
| | 120 days | xxx.x | xxx.x | x.xxx | xx.x | xx.x-xx.x |

N = XX (number of subjects in the Safety Population)

Table with similar format:

Table 88: Logistic Regression Model to Evaluate the Relationship of Study Vaccination with Reporting Any Systemic Event Post Second Study Vaccination, Safety Population

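### The solicited-event model omits each subject's graded dose-1 reaction; once the outcome is settled, adding it would sharpen the BoostDose comparison by an amount that depends on a correlation the documents do not give

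*SAP*

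**What the plan says.** Solicited reactogenicity is a primary safety endpoint (SAP 3.2.1). For its between-arm analysis, SAP 9.3.1 says "Logistic regression models will be fit to estimate the effect of prime-boost combination", boost dose and interval. The between-arm model in SAP 9.3.1 contains PrimeBoost, BoostDose, Interval, and the interactions of PrimeBoost with each of the other two. No covariate appears in the equation or in the Table 87 shell. By contrast, SAP 8.3.2 says of the antibody models: "All models will be fit with and without adjustment for the following covariates".

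The outcome is defined in two ways. The text of SAP 9.3.1 models the effects "on the probability of reporting any local event or reporting any systemic event after either vaccination". The Table 87 shell is titled for "Reporting Any Local Event Post Second Study Vaccination, Safety Population", and Table 88 does the same for systemic events.

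All six groups receive 3.75 mcg HA with AS03 at dose 1: the 2013 antigen in Groups 1-3 and the 2017 antigen in Groups 4-6 (SAP 4.4.4, 4.4.5). Reactions are graded 0-3 for 7 days after each dose, and the earliest boost is 21 days after the first. SAP 9.3.1 pairs the two doses only in McNemar's test within groups.

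**The concern.** A subject's reaction to the first injection may predict the reaction to the second. It is recorded on everyone before the boost, and the between-arm model does not use it.

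Within a priming antigen, the dose-1 product is the same at every level of BoostDose and Interval, and both factors take effect only at dose 2. For those two effects, dose-1 severity is therefore a baseline value. It is not one for PrimeBoost, because the priming antigen is what PrimeBoost varies.

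The arms hold 30 subjects each, so the tolerability comparison of the two boost formulations is imprecise. The model's p-values also decide what else is analysed. The Table 87 note begins "If statistically significant effects (defined as p-value <0.05) are observed in the model for local events" and then calls for a further model for each individual local event; Table 88 does the same for systemic events.

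**Working it through.** **The plan's own power figure.** SAP section 5 and Table 8 give 80% power with 27 per group at alpha 0.05, "using a two-sided Likelihood Ratio Test". Exact binomial enumeration of that test gives 81.6, 79.4, 80.5, 81.3 and 80.1% for the five rows, so the table reproduces. It concerns antibody responders. The documents give no power for the solicited-event model.

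**Inputs from the documents.** Six equal arms of 30. With the 10% loss that the SAP assumes for the per protocol analysis, used here for subjects reaching dose 2, 27 remain per arm. In a main-effects model, BoostDose compares Groups 2+5 with 3+6, and Interval compares Groups 1+4 with 2+5. Each is 2 x 27 = 54 v 54.

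**Inputs assumed, because the documents give none.**
- Dose-2 reaction rates (unadjuvanted at 120 days / adjuvanted at 120 days / adjuvanted at 21 days): 30/55/80, 45/70/90, 55/80/95 and 70/90/98%. The dose-1 rate equals the adjuvanted 120-day rate.
- Latent dose-1/dose-2 correlation rho: 0, 0.3, 0.5, 0.7. On the yes/no scale these are correlations of about 0, 0.11-0.18, 0.21-0.30 and 0.34-0.44.

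**Method.** Latent reactions z1 and z2 = rho*z1 + sqrt(1 - rho^2)*e are standard normal, and an event occurs when z < Phi^-1(rate). Logistic regression uses likelihood-ratio tests at 0.05, with and without the dose-1 reaction (yes/no or graded), in 3,000 trials per scenario. The Monte Carlo standard error is about 0.8 points per power figure.

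**Gain in power, in points, for the post-second-vaccination outcome (main-effects model).**

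| rho | BoostDose | Interval |
|---|---|---|
| 0 | -0.4 to +0.3 | -0.5 to +0.2 |
| 0.3 | +1.0 to +2.7 | -0.4 to +1.4 |
| 0.5 | +2.8 to +6.8 | -0.6 to +4.3 |
| 0.7 | +6.8 to +13.0 | +2.4 to +8.6 |

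Example at 45/70/90%, rho 0.5, yes/no covariate: BoostDose 76.1 to 81.1%, Interval 76.4 to 80.1%. Near ceiling (70/90/98%, rho 0.5), Interval goes from 52.7 to 52.5%. A second simulation of the same six-arm design gave 1-3, 4-7 and 9-14 points on BoostDose at rho 0.3, 0.5 and 0.7. For Interval at rho 0.5 it gave 3-5 points, and none when adjuvanted rates are 90-98%.

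**With the SAP's interaction terms, rho 0.5 (two rate sets, yes/no covariate).** BoostDose rises from 46.7-47.0 to 52.3-53.0%, and Interval from 48.9-53.0 to 52.5-56.1%.

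**Type I error.** 5.0-5.7% with the covariate.

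**PrimeBoost.** Assume dose-1 rates of 55 v 75% by priming antigen and no true PrimeBoost effect at dose 2. Adjustment moves the PrimeBoost odds ratio from 1.0 to 1.42 (rho 0.5) or 1.75 (rho 0.7), with 17% and 31% false positives.

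**The outcome wording.** If the outcome counts events after either dose, the dose-1 reaction is part of it. At 30/55/80 and 45/70/90% with rho 0.3-0.7, unadjusted BoostDose power falls from 75-77% (second dose only) to 15-23%, and Interval from 77-82% to 33-47%.

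**The case against.** An unadjusted model of randomised arms is valid. The SAP disclaims any powered hypothesis and describes this model as estimation. The antibody models in SAP 8.3.2 do not adjust for the dose-1 response either. All of that stands, so this is an optional refinement and not an error.

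On the log-odds scale that Tables 87-88 report, adjustment does not shrink the standard error. In a 54 v 54 check at 65 v 40%, the median rose from 0.40 to 0.42, 0.45 and 0.47 at observed correlations of about 0.22, 0.37 and 0.44. Power rises because the conditional odds ratio lies further from 1. That is right for the odds ratio, but the gain is not an artefact of scale: the standard deviation of the standardised risk difference falls by about 4-7% at rho 0.5.

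The covariate is also narrower than 0-3 suggests. Protocol 5.2.3 withholds dose 2 after certain Grade 3 reactions to dose 1, so the top grade is largely absent among boosted subjects.

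Two stronger readings are tempting. A reader might infer that the plan gives up several points of power on both effects as a matter of fact. The documents contain no correlation and no reaction rates, and for Interval the gain can be nil. A reader might also take BoostDose as the effect of AS03 alone; the HA dose changes with it, from 3.75 to 15 mcg.

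**Conclusion.** The point holds as a low-priority improvement. The only between-arm model of a primary safety endpoint ignores a predictor that is complete before the boost and valid for two of its three factors.

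Under the assumed rates and 27 per arm, the benefit for BoostDose is about 1-3 points of power at latent correlation 0.3, 3-7 at 0.5 and 7-14 at 0.7. For Interval it is about 0-5 points at 0.5, and none there near ceiling. At zero correlation nothing is lost. These are conditional figures, not a measured loss.

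The point does not extend to PrimeBoost, for which the dose-1 reaction is post-treatment. It applies only to the post-second-vaccination outcome. The conflict between the SAP 9.3.1 text and Tables 87-88 has to be settled first, and in the scenarios examined it affects power far more than the missing covariate does.

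**What to change.** 1. Reconcile the outcome in SAP 9.3.1 with the titles of Tables 87-88. Dose-1 severity can be a covariate only if the outcome is restricted to events after the second vaccination.
2. Keep the unadjusted model, and read PrimeBoost from it.
3. Prespecify a second version that adds each subject's maximum dose-1 severity in the same event class (local or systemic). Read it only for BoostDose and Interval.
4. Report a standardised risk difference beside the conditional odds ratio.
5. Note in the table footnotes that the adjusted odds ratio is conditional on dose-1 severity, and that few boosted subjects will have the top grade.

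The cost is one extra model per table from data already collected, with no added visits or subjects. The drawback is that different coefficients are read from two models, so the SAP must say in advance which model serves which effect.

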[Implementation Note: If statistically significant effects defined p-value <0.05 are observed in the model for systemic events then this table should be repeated for additional models which will be fit for each individual systemic event. Any solicited systemic event grade 1 or higher reported within 7 days of study vaccination will count as a reported event.]

Table 89: Number and Percentage of Subjects Experiencing Solicited Events by Symptom, Maximum Severity and Study Group (Safety Population) – Post Any Study Vaccination

| Symptom | Severity | Group 1 2013 3.75+AS03/ 2017 3.75+AS03 (D1-D22) (N=X) | | Group 2 2013 3.75+AS03/ 2017 3.75+AS03 (D1-D121) (N=X) | | Group 3 2013 3.75+AS03/ 2017 15 (D1-D121) (N=X) | | Group 4 2017 3.75+AS03/ 2017 3.75+AS03 (D1-D22) (N=X) | | Group 5 2017 3.75+AS03/ 2017 3.75+AS03 (D1-D121) (N=X) | | Group 6 2017 3.75+AS03/ 2017 15 (D1-D121) (N=X) | | All Subjects (N=X) | |
|----------------------|----------|--|---------------|---|---------------|--|---------------|--|---------------|---|---------------|--|---------------|-----------------------|---------------|
| | | n | % (95% CI) | n | % (95% CI) | n | % (95% CI) | n | % (95% CI) | n | % (95% CI) | n | % (95% CI) | n | % (95% CI) |
| Any Symptom | None | x | xx (xx-xx) | x | xx (xx-xx) | x | xx (xx-xx) | x | xx (xx-xx) | x | xx (xx-xx) | x | xx (xx-xx) | x | xx (xx-xx) |
| | Mild | x | xx (xx-xx) | x | xx (xx-xx) | x | xx (xx-xx) | x | xx (xx-xx) | x | xx (xx-xx) | x | xx (xx-xx) | x | xx (xx-xx) |
| | Moderate | x | xx (xx-xx) | x | xx (xx-xx) | x | xx (xx-xx) | x | xx (xx-xx) | x | xx (xx-xx) | x | xx (xx-xx) | x | xx (xx-xx) |
| | Severe | x | xx (xx-xx) | x | xx (xx-xx) | x | xx (xx-xx) | x | xx (xx-xx) | x | xx (xx-xx) | x | xx (xx-xx) | x | xx (xx-xx) |
| Any Systemic Symptom | None | x | xx (xx-xx) | x | xx (xx-xx) | x | xx (xx-xx) | x | xx (xx-xx) | x | xx (xx-xx) | x | xx (xx-xx) | x | xx (xx-xx) |
| | Mild | x | xx (xx-xx) | x | xx (xx-xx) | x | xx (xx-xx) | x | xx (xx-xx) | x | xx (xx-xx) | x | xx (xx-xx) | x | xx (xx-xx) |
| | Moderate | x | xx (xx-xx) | x | xx (xx-xx) | x | xx (xx-xx) | x | xx (xx-xx) | x | xx (xx-xx) | x | xx (xx-xx) | x | xx (xx-xx) |
| | Severe | x | xx (xx-xx) | x | xx (xx-xx) | x | xx (xx-xx) | x | xx (xx-xx) | x | xx (xx-xx) | x | xx (xx-xx) | x | xx (xx-xx) |
| Fever | None | x | xx (xx-xx) | x | xx (xx-xx) | x | xx (xx-xx) | x | xx (xx-xx) | x | xx (xx-xx) | x | xx (xx-xx) | x | xx (xx-xx) |

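### Between-arm models for individual solicited reactions are fitted only after a significant composite, so a difference in one reaction can go without a between-arm estimate

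*SAP*

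**What the plan says.** Solicited reactions are a primary safety endpoint (SAP 3.2.1), stated as occurrence with no between-arm test named.

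SAP 9.3.1 models the probability of any local and of any systemic event on prime-boost combination, boost dose, interval and two interactions. Models for single reactions are conditional: "If statistically significant effects are observed in the model for local events or systemic events, then additional models will be fit for each individual event". The sentence ends with a restriction to the same type ("additional models will be fit for each individual event of that type"), so there are two separate conditions. One governs 6 local reactions, the other 8 systemic reactions.

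The implementation notes in Appendix 1 repeat the rule. For Table 87: "If statistically significant effects (defined as p-value <0.05) are observed in the model for local events then this table should be repeated". For Table 88, if significant effects "are observed in the model for systemic events then this table should be repeated for additional models".

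Whatever the composite shows, Tables 84-86 give number, percentage and Clopper-Pearson 95% CI by arm for every reaction. Tables 89-91 add maximum severity with intervals, and Tables 92-94 severity by day. McNemar's test (Tables 95-96) compares dose 1 with dose 2 within an arm.

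Protocol 11.6.2 permits chi-square or Fisher comparisons of symptom proportions between arms, with no preceding condition. The SAP does not carry this option over, and its Section 12 declares no changes from the protocol's analyses. SAP 6.8 says that no specific null hypothesis is tested and no multiplicity adjustment is made.

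**The concern.** The logistic models are the only between-arm comparison of solicited reactions in the SAP. The condition means that a single reaction gets a between-arm estimate only if the composite of its type shows a significant term first.

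A composite is a weak screen for this. A subject who already reports pain or fatigue counts as having an event whether or not swelling or fever is added. A difference confined to one reaction is therefore diluted by whatever reactions are common in all arms. The reader would then have six separate rates with intervals, and would have to judge the contrast by eye.

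A two-stage rule is usually justified by control of false positives. That does not apply here, because the SAP claims no such control.

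**Working it through.** **Inputs from the documents.** 30 per arm, 180 in total, equal allocation; 6 local and 8 systemic reactions; threshold p<0.05. The SAP's sample-size section uses 27 per arm because "It is assumed that up to 10% of subjects ($N=3$) will be excluded from the per protocol analysis". That concerns immunogenicity. Safety analyses use all vaccinated subjects, so 30 per arm is the relevant figure.

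**The plan's own between-arm power figure.** SAP Table 8 gives detectable differences for immune responders at 80% power, 27 v 27, two-sided likelihood-ratio test. Exact enumeration at its five pairs gives power of 0.816, 0.794, 0.805, 0.813 and 0.801, so the table reproduces. There is no corresponding figure for reactions.

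**Assumed scenario.** One reaction occurs in 25% after the 3.75 mcg + AS03 boost and 5% after the 15 mcg boost, independently of the other reactions of its type. Those others give a background rate q.

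Composite rate = 1 − (1 − q)(1 − e), with e = 0.25 or 0.05. The composite difference is therefore (1 − q) × 0.20.

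| q | AS03 boost | 15 mcg boost | Difference |
|---|---|---|---|
| 0.50 | 62.5% | 52.5% | 10 points |
| 0.70 | 77.5% | 71.5% | 6 points |
| 0.90 | 92.5% | 90.5% | 2 points |

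A 20-point difference in the reaction becomes 10, 6 or 2 points in the composite.

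**How often the condition is met.** Simulated, counted as met if any treatment term has |z| > 1.96 (Wald), 30 per arm:

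| q | Six-parameter model of SAP 9.3.1 | Three main effects, as in the Table 87-88 shells |
|---|---|---|
| 0.50 | 24% | 31% |
| 0.70 | 17% | 19% |
| 0.90 | 2% | 9% |

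Repeat runs differ by up to about 4 points. At 27 per arm the figures are 19/17/1% and 27/20/7%.

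**Direct comparison of the same reaction.** Fisher's exact test of 25% v 5% has 79% power at 54 v 54 and about 85% at 60 v 60 (Groups 2+5 v 3+6).

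**If the composite itself moves.** At 90% v 60% the condition is met in about 73% (six-parameter) to 98% (main effects) of trials.

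**If nothing differs.** The condition is still met in roughly 12% to 17% of trials at composite rates of 50% to 70%, because any of several terms can trigger it. Three independent tests at 0.05 would give 1 − 0.95³ = 14%.

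**Time window.** The text of SAP 9.3.1 counts events after either dose; the titles of Tables 87-88 count only those after the second. Every arm receives AS03 at dose 1. If dose 1 produces the AS03-boost rates in all arms, independently of dose 2, then at q = 0.50 the either-dose composite is 1 − 0.375² = 85.9% v 1 − 0.375 × 0.475 = 82.2%. The 10-point difference shrinks to under 4.

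**The case against.** The strongest reply is that little is withheld. The primary endpoint is occurrence, and occurrence is fully reported: every reaction, by arm, with exact intervals, after either and each dose. What is conditional is a follow-up model in a study that sets out to estimate, not to test. This stands. A reader might infer that the SAP lets a non-significant composite stand for no difference on all 14 reactions. The documents do not support that. No sentence equates the two, and the rule is type-specific, so all 14 go unmodelled only if both conditions fail.

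Second, the scenario is selective. Protocol 2.3.1 describes AS03 as raising several injection-site reactions and solicited rates generally. A broad shift moves the composite, and the individual models then usually follow. This also stands: a reader might infer that individual comparisons would usually be missing, but that holds only for an isolated difference against a common background.

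Third, the power comparison mixes two effects. For 25% v 5% at 27 per arm, the boost-dose term of the six-parameter model, fitted with no condition, has only about 29% power, against 78% with main effects only. Part of the gap from 85% is therefore parameterisation rather than the condition. With main effects the gap remains large.

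Fourth, the protocol already permits an unconditional test. It is optional there and absent from the SAP, so omitting it breaches nothing, but it also guarantees nothing.

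**Conclusion.** The point holds in limited form. Under the SAP as written, an individual solicited reaction gets a between-arm estimate only if the composite of its type has a term with p<0.05. When one reaction differs against a common background, that happens in about 2% to 31% of trials at 30 per arm, while a direct 60 v 60 comparison has about 85% power. When the composite shifts from 60% to 90%, it happens in about 73% to 98%.

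These figures rest on assumed reaction rates, independence between reactions, Wald tests and events counted after dose 2 only. The direction depends on none of the particular values, because the composite difference is always the single-reaction difference multiplied by (1 − q).

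The condition has no error-control role and narrows what the protocol allows without Section 12 saying so. Since arm-level rates and intervals appear anyway, this is a cheap improvement rather than a flaw in the primary safety reporting.

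**What to change.** 1. Delete the condition from SAP 9.3.1 and from the implementation notes to Tables 87 and 88.
2. For each of the 14 solicited reactions, report the between-arm contrasts after dose 2 with 95% CIs, whatever the composite shows:
   - boost formulation at the 4-month interval: Groups 2+5 v 3+6;
   - prime: Groups 1+2+3 v 4+5+6;
   - interval with the adjuvanted boost: Groups 1+4 v 2+5.
   
   A risk difference is convenient with sparse counts, but the interval matters more than the scale.
3. Add a sentence that p>0.05 is not evidence of no difference, and that the interval shows what excess has not been ruled out.
4. Reconcile the either-dose window in SAP 9.3.1 with the second-dose window in the titles of Tables 87-88.
5. Restore the protocol's unconditional comparison or record its replacement in Section 12.

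The cost is SAP wording and 14 × 3 = 42 short programmed contrasts on data already collected. The downside is more unadjusted intervals in the report, in a study that already states it makes no adjustment.
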